2.4. CCR2 Inhibitor CCX140-B: Non-Clinical Safety

The nonclinical safety of CCX140-B was studied *in vitro* and *in vivo* in mice, rats, dogs and Cynomolgus monkeys. The nonclinical toxicity studies with CCX140-B were supplemented with safety pharmacology studies including behavioral and autonomic neuronal function testing, pulmonary and cardiovascular function evaluations in conscious rats and dogs, and included an *in vitro* potassium channel hERG assay. There were no adverse findings attributable to CCX140-B in any of the organ systems studied. In addition studies of the effects of CCX140-B on the immune system (T cell dependent antibody production) were also conducted and did not identify any safety concerns. CCX140-B was not genotoxic *in vitro* or *in vivo*, and was not phototoxic *in vitro*.

In repeat-dose toxicity studies (up to 26 weeks in rats and 39 weeks in dogs) two adverse nonclinical findings of concern were revealed: **changes in** red blood cell [RBC] parameter findings, with reticulocytosis, which was observed across all species studied, and peripheral axon neuropathy which was observed only in dogs.

In these repeat dose nonclinical studies, there was clear evidence of rapid recovery of the RBC findings and reticulocytosis in the absence of drug. In the 39-week dog study, the highest dose (**50 mg/kg**) of CCX140-B was associated with slight to mild neuronal cell changes (based on thorough histological examinations), but these were not deemed to be of likely clinical relevance by the histopathologist and indeed there were no clinical correlates observed. Cessation of active damage (decreased immune cell infiltrates) was noted, however recovery was incomplete. Off-target binding assays, *in vivo* immune mechanism, and immunohistochemistry evaluations did not reveal a mechanism for the neuropathy findings in dogs, but may rule out direct CCR2 receptor inhibition. In *in vitro* assessments, there were no unique metabolites to dogs. However,

in dogs there is a higher percentage of free CCX140 in plasma which is unique among studied species, including humans. The neuronal findings appearing only in dogs suggests species specificity, however the mechanism is unknown, and a threshold effect of free drug concentration cannot be ruled out.

The changes in RBC parameter findings are likely translatable to humans, but are monitorable, reversible, and there was an acceptable safety margin across all species (see below). To ensure early detection of **changes in RBC parameters** in the Phase 2 clinical trial, blood samples will be drawn at baseline, at 6 hours following administration of the first dose, at Study Days 8, 15 and 29, then at every 4 week intervals throughout the treatment and follow up period for assessment of complete blood count, reticulocyte count and bilirubin.

Neuropathy findings in dogs are likely species-specific with a higher safety margin than **the changes in RBC parameters**, however reversibility was incomplete and the mechanism is unknown. Subjects in the Phase 2 study will be monitored for adverse events related to the nervous system, and will be **examined for vibration-sense deficits and** evaluated for early symptoms using a questionnaire validated for early detection of peripheral neuropathy in studies of patients with HIV infection.

The NOAEL in the 26-week rat studies of 15 mg/kg/day (based on reversible **changes in RBC parameters**) was associated with systemic AUC₀₋₂₄ total plasma exposures to CCX140 of 464.6 and 493.7 $\mu\text{g}\cdot\text{hr}/\text{mL}$, for males and females, respectively. Thus, for dose escalation in human subjects, exposures to CCX140 should not exceed total plasma AUC₀₋₂₄ exposures of 465 $\mu\text{g}\cdot\text{hr}/\text{mL}$, or total C_{max} concentrations of 32 $\mu\text{g}/\text{mL}$.

Results from all the safety and toxicology studies support repeated dosing of CCX140-B to humans up to predicted exposure parity with the 26-week rat NOAEL levels. The NOAEL in the 26-week rat study was associated with systemic exposure to CCX140 which was approximately 3- to 4-fold the predicted human exposure with a 15 mg twice daily (b.i.d.) dose of CCX140-B.

2.4.1. CCR2 Inhibitor CCX140-B: Clinical Experience

CCX140-B is an orally administered, selective small molecule inhibitor of the chemokine receptor known as CCR2. To date it has not been administered in subjects with biopsy-proven FSGS.

CCX140-B has been assessed in 4 Phase 1 clinical trials in healthy volunteers, one Phase 2 trial in subjects with diabetes, and two Phase 2 trials in subjects with diabetic nephropathy. A tabular summary of clinical studies conducted with CCX140-B and submitted to IND 114469 are provided in the Investigator's Brochure.

Efficacy findings in study CL005_140 in patients with diabetic nephropathy and proteinuria provide support for exploring CCX140-B in FSGS. In that trial, 192 subjects with diabetic nephropathy received uninterrupted dosing for up to 52 weeks with placebo, 5 mg daily of CCX140-B or 10 mg daily of CCX140-B. Compared to placebo, CCX140-B was associated with greater reduction in albuminuria. Specifically, changes from baseline in the ratio of urinary albumin to creatinine (UACR) averaged -2% in the placebo group (95% CI -11% to +9%), -18% in the CCX140-B 5 mg group (95% CI -26% to -8%), and -11% in the CCX140-B 10 mg group (95% CI -20% to -1%). The decrease in UACR was observed at the earliest measured time point (Day 15) and reached a maximum decrease by the Day 85 visit (de Zeeuw et al., 2015).

Of note, subjects entering the study were stratified based on the level of proteinuria at baseline. In a pre-specified subset analysis, the greatest percentage improvement in UACR from baseline was observed in subjects who presented with the highest baseline UACR (801-3000 mg/g) and eGFR of at least 60 mL/min/1.73m². In this subset mean changes in UACR from baseline were +45 % in the placebo group (95% CI -6% to +121%, n=8), -23% in the CCX140-B 5 mg group (95% CI -55% to +32%, n=5; p = 0.03 vs control), and -39% in the CCX140-B 10 mg group (95% CI -61% to -7%; n=8; p = 0.004 vs control).

When taken together with results from the pre-clinical studies, and a favorable clinical safety profile (see Investigator's Brochure), these observations further support evaluation of CCX140-B in highly proteinuric renal diseases, including FSGS.

3. OBJECTIVES

3.1. Primary Objective

The primary safety objective of this study is to evaluate the safety and tolerability of CCX140-B in subjects with FSGS with proteinuria.

The primary efficacy objective of this study is to evaluate the effect of CCX140-B treatment on urinary protein excretion in subjects with FSGS, as assessed by change from baseline in the urine protein to creatinine ratio (UPCR) **at Week 12**.

3.2. Secondary Objectives

- To evaluate the effect of CCX140-B on renal function, as assessed by estimated glomerular filtration rate (eGFR) using the CKD-EPI Cystatin C equation, CKD-EPI (**chronic kidney disease epidemiology collaboration**) Creatinine equation, CKD-EPI Creatinine-Cystatin C equation and MDRD (**Modification of Diet in Renal Disease**) Creatinine equation assessed at Weeks 12 and 24
- **To evaluate the effect of CCX140-B treatment on fraction of subjects achieving complete and partial renal remission (by 2 different partial remission definitions)**
- To evaluate the pharmacokinetics (PK) profile of CCX140-B in subjects with FSGS

3.3. Exploratory Objectives

To evaluate the effect of CCX140-B on urinary monocyte chemoattractant protein-1 (MCP-1) and other serum and urinary markers of renal function and inflammation;

To explore the effect of CCX140-B on levels of blood monocytes, T, B and NK cells, and other blood and urinary markers potentially associated with CCR2 antagonism;

To explore the effect of CCX140-B on Health-related Quality of Life changes based on Short Form 36 version 2 (SF-36 v2) and **EuroQuality of Life-5 Domains-5 Levels (EQ-5D-5L) questionnaires**;

To explore the relationships among exposure (PK) of CCX140-B, serum albumin level, and UPCR.

4. STUDY DESIGN

This study will evaluate the efficacy, safety, tolerability, and pharmacokinetics of up to 12 weeks of treatment with each of three dose regimens of CCX140-B or placebo, when used in combination with stable standard of care therapy in subjects with FSGS with significant proteinuria, assessed as $UPCR \geq 1g/g$ at Screening. Following the 12-week blinded treatment period, **the study will evaluate up to 24 weeks of treatment with CCX140-B: all subjects who remain eligible** will receive active treatment for an additional 12 weeks to assess safety and durability of effect.

The target is to enroll 40 male or female subjects in this randomized, double-blind, placebo-controlled, Phase 2 study. Randomization will be stratified by **UPCR <3.5 g protein/g creatinine versus UPCR ≥3.5 g protein/g creatinine at baseline using the screening UPCR** and by the use of glucocorticoids and/or immunosuppressive medications (yes, no).

Subjects will be randomized 1:1:1:1 to one of four treatment groups:

- Group A: Placebo (N=10)
- Group B: CCX140-B 5 mg once daily (N=10)
- Group C: CCX140-B 10 mg twice daily (N=10)
- Group D: CCX140-B 15 mg twice daily (N=10)

Study medication will be taken by the subjects for 84 days, as follows:

- Group A: Three placebo tablets, taken twice daily;
- Group B: One 5 mg CCX140-B tablet and two placebo tablets in the morning; three placebo tablets in the evening;
- Group C: Two 5 mg CCX140-B tablets and one placebo tablet, taken twice daily
- Group D: Three 5 mg CCX140-B tablets, taken twice daily

All subjects will take blinded **oral** study medication **twice daily, 3 tablets** in the morning and **3 tablets in the evening**, with or without food, for **12 weeks** (84 consecutive days). Following the 84-day blinded dosing period, all subjects **who remain eligible** will take open label CCX140-B for an additional **12 weeks** (84 consecutive days) at the highest **tolerated** dose under evaluation, currently planned to be 15 mg twice daily. **The decision on the dose for the open-label period will be made** by the Sponsor, with the advice of the unblinded Data Monitoring Committee (DMC). **After completion of treatment for whatever reason, including early termination**, all subjects are expected to return at 2, 7 and 14 days after taking the last dose of study medication **for assessment of elimination phase PK and 28 days after taking the last dose of study medication for PK and safety monitoring**.

The screening period will be up to 28 days. All potential study subjects must sign written informed consent before any study screening procedures. Diagnosis of FSGS will be confirmed based on clinical judgment supported by a historical or current renal biopsy with characteristic features and/or presence of high-risk genetic variants. Other screening procedures include collection of demographic and medical history, physical examination and vital signs, 12-lead

ECG, serum chemistry including serum albumin and creatinine, hematology, urinalysis including assessment of urinary protein:creatinine ratio (UPCR) and urinary albumin:creatinine ratio (UACR) in a sample from a first morning void, viral and TB screening, pregnancy testing for all female subjects of childbearing potential, and recording of concomitant medication use. For subjects without prior biopsy to confirm diagnosis, needle biopsy may be completed during the screening period. For subjects without genetic screening for risk alleles associated with FSGS, genetic testing may be done during the screening period.

During the treatment period, eligible subjects will visit the study center on Study Days 1, 8, 15, 29 (Week 4), and Weeks 8, 12 (primary endpoint), 13, 16, 20, and 24 for study procedures including interval history, physical examination and vital signs, ECG, study questionnaires, and collection of blood and urine. **A 24 hour urine collection will be done the day before the Day 1 visit (baseline), the day before the Week 12 visit at the end of double-blind dosing, and the day before the Week 24 visit at the end of open-label dosing.** Subjects will return for a follow-up safety visit 4 weeks after the last dose of study drug (at Week 16 for those not entering the open-label phase, or at Week 28 for those who continue dosing into the open-label phase). When feasible, upon discontinuation of treatment for any reason, a sample of whole blood should be collected for assessment of elimination PK at 2, 7 and 14 days after the final dose of **study drug** (CCX140-B or placebo).

For assessment of adverse events of special interest, study procedures will include

- Complete blood count with differential, morphology assessment, reticulocytes count, hemoglobin, LDH, and bilirubin (**total and indirect**) to assess early evidence of hemolysis;
- The AIDS Clinical Trials Group Brief Peripheral Neuropathy Screening Tool Brief Peripheral Neuropathy Screening Tool (ACTG-BPNST) to assess early evidence of neuropathy;
- Monitoring for adverse events of infection;
- Alkaline phosphatase, ALT, AST and bilirubin (**total and direct**); to assess for evidence of drug induced liver injury.

For assessment of pharmacokinetics, study procedures will include

- Seven blood samples collected over 6 hours on Study Day 1 and at steady state (Study Day 15, or within 2 weeks thereafter) to assess AUC_{0-6} following the first administration of study drug, and at steady state;
- Assessment of C_{min} at intervals to ensure that exposure is within the projected range, with adequate safety margin based on the NOAEL established in preclinical toxicology;
- Upon discontinuation of treatment for any reason, collection of blood at 2 days, 7 days and 14 days following discontinuation to assess elimination.

All study procedures are presented in the [Time and Events table](#).

Subjects who are using an angiotensin converting enzyme (ACE) inhibitor, angiotensin receptor blocker (ARB) or other blocker of the renin angiotensin aldosterone system (RAAS), or who are using glucocorticoids, a calcineurin inhibitor or other immunomodulatory or immunosuppressive

[figure not shown]
therapy, should be on a stable dose for at least 4 weeks prior to screening. The dose of these medications must be kept constant over the course of the study in order to prevent undue influence of changes in these medications on the efficacy and safety assessments except when adjustment is required for patient well-being. The investigator must also attempt to keep doses of other medications, and lipid-lowering medications fixed throughout the blinded study period in order to prevent undue influence of changes in these medications on the efficacy and safety assessments.

Subjects who experience deteriorating renal function based on an increase in serum creatinine of at least 50% (confirmed by a repeat measurement after 2 weeks) which is otherwise not explained (e.g., dehydration, new medication), or increase in UPCR of >3.0 g/g (confirmed by a repeat measurement after 2 weeks) during the 12-week treatment period, will exit the treatment phase of the study and be treated at the discretion of the treating physician. All subjects who discontinue treatment will remain in the study for follow up and outcome recording.

An independent Data Monitoring Committee (DMC) will be responsible for reviewing safety data throughout the course of the study.

Subjects will be discharged from the study at the completion of the Week 28 visit. To the extent possible, any adverse events that are deemed study drug-related and are ongoing at discharge will be followed-up to resolution or until a determination is made that the unresolved event is stable.

Figure 1: Study Schema

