All study procedures are presented in the [Time and Events table](#).

Subjects who are using an angiotensin converting enzyme (ACE) inhibitor, angiotensin receptor blocker (ARB) or other blocker of the renin angiotensin aldosterone system (RAAS), or who are using glucocorticoids, a calcineurin inhibitor or other immunomodulatory or immunosuppressive therapy, must be on a stable dose for at least 4 weeks prior to screening. The dose of these medications should be planned to be kept constant over the course of the study in order to prevent undue influence of changes in these medications on the efficacy and safety assessments, except when adjustment is required for patient safety. The investigator must also attempt to keep doses of other medications, and lipid-lowering medications fixed throughout the blinded study period in order to prevent undue influence of changes in these medications on the efficacy and safety assessments.

Subjects who experience deteriorating renal function based on an increase in serum creatinine of at least 50% (confirmed by a repeat measurement after 2 weeks) which is otherwise not explained (e.g., dehydration, new medication), or increase in UPCR of >3.0 g/g (confirmed by a repeat measurement after 2 weeks) during the 12-week treatment period, will exit the treatment phase of the study and be treated at the discretion of the treating physician. All subjects who discontinue treatment will remain in the study for follow up and outcome recording.

An independent Data Monitoring Committee (DMC) will be responsible for reviewing unblinded safety data throughout the course of the study.

Subjects will be discharged from the study at the completion of the Week 28 visit. To the extent possible, any adverse events that are deemed study drug-related and are ongoing at discharge will be followed-up to resolution or until a determination is made that the unresolved event is stable.

Number of Subjects

The target number of subjects is 40. Subjects who discontinue during the first 14 days of taking study drug for reasons other than adverse events related to study drug may be replaced to ensure that sufficient data are available for assessment of safety, PK, and efficacy.

Main Criteria for Inclusion

1. Male or female subjects aged 18-75 years inclusive
2. Urinary total protein:creatinine ratio (UPCR) ≥ 1 g protein/g creatinine at screening (or UPCR at 113 mg/mmol).
3. Diagnosis of FSGS based on at least one of the following:

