4.2.1. Stopping Guidelines

An independent Data Monitoring Committee (DMC) will be responsible for reviewing safety data throughout the course of the study. Among other responsibilities, the DMC is tasked with implementing dose modification guidelines to assure the safety of all study participants.

Guidelines will be defined for stopping the study, halting enrollment or halting treatment based on safety events occurring in more than 1 subject. General dose modification guidelines for individuals are provided below.

Table 2: Dose Modification Guidelines for Single Subjects

| Assessment | Event | Timing | Response |
|---------------------------------------|---|--|-------------------------------------|
| Serum Creatinine | 50% increase from baseline value | If confirmed by repeat measurement after 2 weeks | Discontinue treatment with CCX140-B |
| Urine Protein:Creatinine ratio (UPCR) | If baseline UPCR < 6.0 g/g an increase of >3.0 g/g; if UPCR \geq 6.0 g/g an increase of 50% | If confirmed by repeat measurement after 2 weeks | Discontinue treatment with CCX140-B |

| Assessment | Event | Timing | Response |
|-----------------------------------|--|--|--|
| ALT, AST | ALT or AST ≥ 8 x ULN | Retest within 72 hours (ALT, ASP, ALP and Total Bilirubin should all be re-tested) | If confirmed, discontinue treatment with CCX140-B |
| ALT, AST | ALT or AST ≥ 5 x ULN for more than 2 weeks | Retest within 72 hours and then 2-3 times per week (ALT, ASP, ALP and Total Bilirubin should all be re-tested) | If confirmed, discontinue treatment with CCX140-B |
| ALT, AST, Total Bilirubin and INR | ALT or AST ≥ 3 x ULN and either Total Bilirubin > 2 ULN or INR > 1.5 | Retest within 72 hours (ALT, ASP, ALP, Total Bilirubin and INR should all be re-tested) | If confirmed, discontinue treatment with CCX140-B |
| ALT, AST | ALT or AST ≥ 3 x ULN with the appearance of fatigue, nausea, vomiting, right upper quadrant pain or tenderness, fever, rash and /or eosinophilia ($>5\%$) | | Discontinue treatment with CCX140-B |
| LDH | LDH ≥ 2 times upper limit of normal, and confirmed to not be related to specimen handling | Halt treatment then reassess after 2 weeks | If within normal range, continue to treat at reduced dose, defined as the next lower dose. Otherwise, contact Medical Monitor to discuss next steps |

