5.2. Inclusion Criteria

Subjects must meet all the following inclusion criteria to enter the study:

1. Male or female subjects aged 18-75 years inclusive.
2. Urinary total protein:creatinine ratio (UPCR) ≥ 1 g protein/g creatinine at screening (or UPCR at 113 mg/mmol).
3. Diagnosis of FSGS based on at least one of the following:
 - Renal biopsy demonstrating the FSGS lesion and characteristic clinical presentation and course
 - High risk genetic variant and characteristic clinical presentation and course
4. Diagnosis of one of the following subtypes of FSGS:
 - Primary FSGS based on characteristic histopathology, medical history and clinical course, or
 - FSGS secondary to a genetic variant associated with increased risk or severity, which may include NPHS1, NPHS2, WT-1, LAMB2, CD2AP, TRPC6, ACTN4 or INF2
5. Estimated glomerular filtration rate (eGFR) >30 mL/min/1.73m², with eGFR calculated using the Chronic Kidney Disease Epidemiology Collaboration (CKD_EPI) equation (using creatinine or cystatin C)
6. The typical blood pressure of the patient should be clinically stable prior to enrollment and not exceed 145/95 mmHg.
7. If using RAAS blockers, dose must be stable for a minimum of 4 weeks prior to Screening, and projected to remain stable through Study Week 12, unless adjustment is required for management of hypertension.
8. If using immunosuppressive or immunomodulatory therapy, dose must be stable for a minimum of 4 weeks prior to Screening, and projected to remain stable through Study Week 12.
9. If using glucocorticoids, dose must be stable for a minimum of 4 weeks prior to Screening and projected to remain stable through Study Week 12.
10. Female subjects of childbearing potential may participate if adequate contraception is used during, and for at least **1 month** after last dose of study drug. Male subjects with partners of

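### The UPCR rule that ends blinded treatment has two conflicting versions for subjects with baseline UPCR above 6.0 g/g

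*Protocol*

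**What the plan says.** Section 4 (Study Design) of the protocol sets an unconditional rule: a subject with an "increase in UPCR of >3.0 g/g (confirmed by a repeat measurement after 2 weeks) during the 12-week treatment period, will exit the treatment phase". The Methodology part of the Synopsis gives the same criterion, "increase in UPCR of >3.0 g/g (confirmed by a repeat measurement after 2 weeks) during the 12-week treatment period", also with no reference to the baseline level.

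Table 2 in Section 4.2.1 (Stopping Guidelines) splits the rule by baseline. The first branch is "If baseline UPCR < 6.0 g/g an increase of >3.0 g/g". The second is a relative criterion for UPCR at or above "6.0 g/g an increase of 50" per cent. The timing and response columns read "If confirmed by repeat measurement after 2 weeks | Discontinue treatment with CCX140-B". The table is introduced with the sentence "General dose modification guidelines for individuals are provided below".

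Inclusion criterion 2 sets a floor of 1 g/g for screening UPCR and no ceiling, so subjects above 6.0 g/g can be enrolled. No passage says whether Section 4 or Table 2 governs. The SAP does not restate the rule. The amendment summary changes other rows of Table 2 but not the UPCR row, so this is a conflict within current text.

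**The concern.** Both passages end study treatment on the same variable, after the same two-week confirmation, during the same blinded period, but their thresholds part above a baseline of 6.0 g/g. Two sites can each follow the protocol and handle the same patient in opposite ways.

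Two things are at stake. First, this is a subject-protection rule, and confirmed worsening of proteinuria should lead to the same action everywhere. Second, the trigger variable is the primary endpoint. A subject who exits is treated as the treating physician sees fit and stays in follow-up, so the Week 12 UPCR may reflect non-study therapy.

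If such therapy counts as non-allowed, the SAP treats the subject differently from one analysis to the next:

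- The primary MMRM (SAP 3.4.1) has no provision for setting later values aside.
- Sensitivity analysis 3 carries forward the last value before the medication.
- The responder analysis imputes non-response.
- The per-protocol population (SAP 3.2.3) may exclude the subject.

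With 10 subjects per arm, one subject is 10% of an arm. By baseline value, every subject in the conflict zone lies on the ≥3.5 g/g side of the stratification cut.

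**Working it through.** **Inputs.** Section 4 and the Synopsis: stop if the rise exceeds 3.0 g/g. Table 2: stop if the rise exceeds 3.0 g/g when baseline is below 6.0 g/g, and if it reaches 50% when baseline is 6.0 g/g or more. I read the second branch as referring to baseline UPCR and to a rise of at least 50%.

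**Step 1: where the rules part.** For baseline *b* (g/g), the on-treatment UPCR that triggers exit is above *b* + 3.0 under Section 4. Under Table 2 it is above *b* + 3.0 for *b* < 6.0, and 1.5*b* or more for *b* ≥ 6.0. The gap is 1.5*b* − (*b* + 3.0) = 0.5*b* − 3.0, which is zero at *b* = 6.0 and grows with *b*.

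| Baseline (g/g) | Section 4: above | Table 2: at or above | Gap (g/g) |
|---|---|---|---|
| 6 | 9.0 | 9.0 | 0 |
| 7 | 10.0 | 10.5 | 0.5 |
| 8 | 11.0 | 12.0 | 1.0 |
| 10 | 13.0 | 15.0 | 2.0 |
| 12 | 15.0 | 18.0 | 3.0 |
| 15 | 18.0 | 22.5 | 4.5 |

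Below 6.0 g/g the rules are identical. At exactly 6.0 they differ only for a rise of exactly 3.0 g/g.

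**Step 2: one patient.** Baseline 8.0 g/g rising to a confirmed 11.5 g/g is +3.5 g/g, or 3.5/8.0 = 44%. Section 4 and the Synopsis require exit; Table 2 is not met. A rise to 12.5 g/g triggers both rules, and a rise to 10.5 g/g triggers neither.

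**Step 3: how often a reading might cross.** This is an illustration only. It takes the SD of 0.70 for change in log UPCR (Protocol 9.4), no true change and a normal distribution. The SAP (2.2.4) attaches the same 0.70 to the group difference. The stated half-width shows how it was used: with the 90% two-sided *t* value on 18 degrees of freedom, 1.734 × 0.70 × √(2/10) = 0.543, so 0.70 enters as the SD of one subject's change.

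- Section 4: P(Z > ln((*b* + 3)/*b*)/0.70)
  - *b* = 8: ln 1.375 = 0.318; 0.318/0.70 = 0.455; P = 0.325
  - *b* = 10: ln 1.3 = 0.262; 0.262/0.70 = 0.375; P = 0.354
  - *b* = 15: ln 1.2 = 0.182; 0.182/0.70 = 0.260; P = 0.397
- Table 2: P(Z > ln 1.5/0.70) = P(Z > 0.579) = 0.281 at every such baseline

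The rules differ by about 4, 7 and 12 percentage points at baselines 8, 10 and 15. These figures are for a single reading; the required confirmation lowers both sides.

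**The case against.** The strongest reply is that the texts are not strictly opposed. Table 2 lists events that prompt discontinuation and never tells a site to continue below its threshold. Above 6.0 g/g, anything that meets Table 2 also meets Section 4, apart from the single point at exactly 6.0. A site could satisfy both by following Section 4, and Table 2 is presented as guidance. This does not remove the problem: on that reading the second branch of Table 2 does nothing, and a reader cannot tell whether it was meant to replace the general rule at high baselines. A site that takes the more detailed table as controlling has an equally defensible position.

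Several narrower points stand:

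- The conflict is confined to rises above 3.0 g/g but below 50%, not to every subject at or above 6.0 g/g. The number affected among 40 may be small.
- The probabilities in Step 3 are not trigger rates. They ignore confirmation and regression to the mean, and the SD comes from a diabetic nephropathy study.
- Subjects who stop remain in follow-up, and the Medical Monitor is to be contacted (Protocol 5.5), which gives some central control. The SAP has sensitivity, responder and per-protocol handling for non-allowed medication.
- Divergence between sites during blinded treatment occurs without knowledge of the arm, so no direction of bias can be claimed.

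These points limit the likely effect on the treatment comparison. They do not tell a site which rule to apply.

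**Conclusion.** The concern holds. The protocol carries two current, unreconciled UPCR exit criteria that give different answers for any baseline above 6.0 g/g when a confirmed rise exceeds 3.0 g/g but falls short of 50%. The disputed band is 0.5*b* − 3.0 g/g wide: 1.0 at baseline 8, 2.0 at 10 and 4.5 at 15. That result needs only the protocol's own thresholds and the reading of Table 2 given in the working. The crossing probabilities (32%, 35% and 40% against 28%) rest on an SD borrowed from another disease and on single readings; the conclusion does not depend on them. The share of subjects above 6.0 g/g is not given, so the effect on the primary analysis cannot be sized. It must be corrected all the same, because a mandatory stopping rule on the primary variable should have one value.

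**What to change.** Reconcile the Synopsis (Methodology), Section 4 and the UPCR row of Table 2 in Section 4.2.1 so that one UPCR exit criterion appears in all three places. The wording should state whether the criterion depends on baseline and which study period it covers, since Section 4 limits it to the 12-week period and Table 2 names none. Which criterion is right is a decision for the sponsor's clinical team; this review takes no position.

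The cost is a protocol clarification or administrative amendment and a memo to sites. Sample size, visit schedule and analysis model are unaffected. If blinded dosing is already complete, the sponsor should record, for each UPCR-driven discontinuation, which of the two rules was applied.
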